Appendix A Visual Analog Scale

1. Background

Corticosteroid therapy, including intralesional and topical applications, has many indications within the fields of Dermatology, Plastic Surgery, and Orthopedics. However, these injections can be quite painful, which leads many patients to discontinue treatment.

Often, the injection involves a mixture of local anesthetic and corticosteroids despite a lack of evidence that the use of lidocaine improves pain.^{1,2} Due to the acidic pH, the lidocaine component of the injection can actually cause a significant burning sensation during the procedure. Lidocaine does not have anti-inflammatory properties and does not treat the underlying pathology. By including another medication, lidocaine also adds cost and risk to the procedure.

In a double blind, randomized control trial, Osanakornkul and Burusapat studied the benefit of applying topical anesthetics or a 1:1 mixture of 1% lidocaine and triamcinolone acetonide at the injection site to alleviate pain during keloid treatment.² While the use of a topical anesthetic 1 hour prior to the injection was able to alleviate the pain from needle stick, the study did not show a statistical difference in pain outcomes with the use of lidocaine. However, this study was limited to the use of intralesional corticosteroid injections for the treatment of keloids. In addition, the study only focused on 3 locations: the shoulder, sternum, and ear. Keloid injections are often more painful than other injections because the horizontal penetration of the needle can pierce a large number of nerve endings. In routine injections, the entry of the needle is either vertical or angled and thus pierces a small number of nerve endings.³ In addition, the injected material stretches nerve endings and compresses them against unyielding keloid tissue, causing substantial pain that can persist up to several hours after the procedure.³ This study will examine intralesional corticosteroid injections for keloids, alopecia areata, and other indications while including a wider variety of injection sites.

2. Rationale and Specific Aims

The purpose of this study is to see if removing lidocaine from intralesional injections decreases pain of the injection. We hypothesize there will be no difference in pain outcomes if lidocaine is removed from intralesional corticosteroid injections.

3. Animal Studies and Previous Human Studies

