A similar study was conducted in plastic surgery with intraarticular injections for trigger finger. The project examined pain outcomes for injections containing steroid + normal saline vs steroid + local anesthetic. The results indicated that injections containing local anesthetic were significantly more painful. Thus, including a mixed local anesthetic in the injection adds unnecessary cost and risk to the procedure. Because steroid injections in dermatology are also commonly mixed with a local anesthetic, this study design can be applied to these intralesional injections as well.

4. Inclusion/Exclusion Criteria

Inclusion Criteria:

- >12 years old presenting with an indication for intralesional steroid injection

Exclusion Criteria:

- Not a candidate for corticosteroid injection
- Contraindication to lidocaine

5. Enrollment/Randomization

All patients meeting inclusion/exclusion criteria will be offered enrollment. Using a coin flip, patients will have a 50% chance of receiving one of the following treatments:

1. Corticosteroid + lidocaine
2. Corticosteroid + normal saline

6. Study Procedures

Day 1 (In clinic): After diagnosing the need for an intralesional injection, patients will be screened for enrollment. The consent form will be reviewed in depth to describe the purpose and procedures associated with the study. If they agree to be part of the study, we will collect the following demographic information:

- MRN
- Age
- Gender
- Comorbidities (chronic opioid use, smoking, diabetes, neuropathy, fibromyalgia)
- Phone number
- Site of injection (scalp, face, neck, and trunk)
- Indication for injection

The patient will then be randomized to receive one of the following injections:

1. Corticosteroid with normal saline
2. Corticosteroid with lidocaine

A co-investigator will prepare the syringe to ensure blinding. The injection site will be prepped in sterile fashion with an alcohol wipe. The physician will then administer the injection. Immediately following the injection, the patient will be asked to rate the pain of the injection based on the visual analog scale (appendix A). Specifically, the co-investigator will say "Rate the injection experience on a scale of 0 to 10, 0 being no pain and 10 being the worst pain of your life". A bandaid will be placed over the injection site and the patient will be reminded to expect a phone call that afternoon and the next day.

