We are planning a study of a continuous response variable from independent control and experimental subjects with 1.1538 control(s) per experimental subject. In a previous study the response within each subject group was normally distributed with standard deviation 0.3. If the true difference in the experimental and control means is 0.2, we will need to study 34 experimental subjects and 39 control subjects to be able to reject the null hypothesis that the population means of the experimental and control groups are equal with probability (power) 0.8. The Type I error probability associated with this test of this null hypothesis is 0.05.

11. Privacy/Confidentiality Issues

Private health information (PHI) will be used in the study, but not disclosed. All PHI will be stored on a secure, password-locked server. All participants in the study have obtained Human Research certification to have the necessary authorization to PHI. When collecting patient data, only medical record numbers will be used to identify patients.

[figure not shown]
12. Follow-up and Record Retention

The study will last for approximately 1 year after initiation or until the enrollment goal is met. At the study conclusion, all identifiable data will be destroyed and de-identified data will be kept for analysis.

13. References:

2. Usanakornkul, A., & Burusapat, C. (2017). A Topical Anesthetic and Lidocaine Mixture for Pain Relief During Keloid Treatment. *Dermatologic Surgery*, 43(1), 66-73. doi:10.1097/dss.0000000000000932
3. Mishra S Safe and less painful injection of triamcinolone acetonide into a keloid—a technique. *J Plast Reconstr Aesthet Surg* 63:e205

Appendices:

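### Section 10 names no covariate although the Background names keloid as a pain predictor; one prespecified keloid term is a cheap improvement with an expected but not guaranteed gain in precision (low severity)

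*Combined protocol and SAP*

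**What the plan says.** Section 10 (Statistical Plan) opens with "We are planning a study of a continuous response variable from independent control and experimental subjects". It sizes the trial to "reject the null hypothesis that the population means of the experimental and control groups are equal", using "In a previous study the response within each subject group was normally distributed with standard deviation 0.3". It gives 34 experimental and 39 control patients for a difference of 0.2, power 0.8 and type I error 0.05. Neither Section 10 nor any other section names a model, covariate or stratification factor.

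Three other places bear on this:

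- **Section 1 (Background)** states that "Keloid injections are often more painful than other injections". It offers a mechanism, with the injected material "causing substantial pain that can persist up to several hours after the procedure". It then widens the population: "This study will examine intralesional corticosteroid injections for keloids, alopecia areata, and other indications".
- **Section 5 (Enrollment/Randomization)** sets simple randomisation: "Using a coin flip, patients will have a 50% chance of receiving one of the following treatments". Nothing balances the arms on indication.
- **Section 6 (Study Procedures)** lists the indication among the data collected after consent, and places randomisation after that list.

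**The concern.** The protocol names a predictor of pain, broadens enrolment across it and records it at baseline, but plans no use of it. Because indication is recorded before allocation, it is a proper baseline covariate.

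If keloid patients do report more pain, that variation stays in the error term of a plain two-group comparison. The interval for the treatment difference is then wider than the collected data require. The coin flip may also leave the arms with unequal keloid shares. Readers would then ask for an adjusted result, and without a prespecified model any answer would be a post hoc choice.

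What is at stake is some precision and the standing of a later adjustment, not validity.

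**Working it through.** **Inputs.** From Section 10: n = 34 and 39, SD 0.3, difference 0.2, alpha 0.05 (taken as two-sided). Assumed, because the documents do not give them: R², the share of pain variance explained by keloid status; p, the keloid share; g, the mean pain gap between keloid and other indications.

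**1. The plan's own figure.** SE = 0.3 × √(1/34 + 1/39) = 0.3 × 0.2346 = 0.0704. Noncentrality = 0.2/0.0704 = 2.841 on 71 df, so noncentral-t power is 0.800. The stated sample size reproduces with a two-sided test; a one-sided test would need only about 26 + 30. The 95% CI half-width is 1.994 × 0.0704 = 0.1404.

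**2. Adding one keloid term.** The residual variance is multiplied by (1 − R²). Chance imbalance of one covariate inflates the expected variance by 1 + 1/(73 − 4) = 1.0145, and one df is lost (70 left).

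| Assumed R² | Variance ratio (1 − R²) × 1.0145 | CI half-width | Change in CI width | Power |
|---|---|---|---|---|
| unadjusted | 1 | 0.1404 | – | 0.800 |
| 0 | 1.014 | 0.1414 | +0.7% | 0.794 |
| 0.05 | 0.964 | 0.1378 | −1.8% | 0.814 |
| 0.10 | 0.913 | 0.1341 | −4.4% | 0.835 |

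The variance ratio and the relative change in width do not depend on the SD. The power column does.

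**3. Break-even.** (1 − R²) × 1.0145 = 1 gives R² = 1 − 1/1.0145 = 0.0143.

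**4. What R² might be.** If 0.3 is the total SD, R² = p(1 − p)g²/0.09.

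| Keloid share p | g = 0.1: R², power | g = 0.2: R², power |
|---|---|---|
| 5% | 0.005, 0.797 | 0.021, 0.803 |
| 10% | 0.010, 0.798 | 0.040, 0.810 |
| 20% | 0.018, 0.802 | 0.071, 0.823 |
| 30% | 0.023, 0.804 | 0.093, 0.832 |
| 50% | 0.028, 0.806 | 0.111, 0.839 |

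At g = 0.1, break-even needs p(1 − p) = 0.0143 × 0.09/0.01 = 0.129, a share of about 15%. Below that, adjustment costs a little.

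**5. If 0.3 is instead the SD within one indication.** Total SD = √(0.09 + p(1 − p)g²). With g = 0.2 and p from 5% to 50% this is 0.303 to 0.316. Unadjusted power falls to between 0.792 and 0.758, against 0.794 adjusted.

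**6. If the SD on the 0–10 scale is larger.** At R² = 0.10, power for a difference of 0.2 moves from 0.134 to 0.142 at SD 1, and from 0.070 to 0.072 at SD 2. Reaching R² = 0.10 with a 10% keloid share would need a gap of √(0.1/0.09) = 1.05 points at SD 1, or 2.1 points at SD 2. Break-even gaps for shares of 30% down to 5% are 0.26 to 0.55 points at SD 1 and 0.52 to 1.10 at SD 2.

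**7. Chance imbalance.** By exact binomial calculation, the arms differ by at least 15 percentage points in keloid share in 0.6%, 4.1%, 10.8%, 16.4% or 20.2% of trials at shares of 5%, 10%, 20%, 30% or 50%.

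**8. Type I error.** In simulation (100,000 trials per setting, normal errors, no interaction, shares 5% to 50%), it was 0.049 to 0.051 for both analyses.

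**The case against.** The strongest reply is that nothing here is wrong. A two-group comparison after randomisation is unbiased and keeps its type I error. Section 10 does not rule out adjustment; that the analysis is unadjusted is inferred from its silence. All of this stands, and it limits the point to an efficiency suggestion.

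A second reply is that the sign of the gain is open, not only its size. The Background says only that keloid injections are often more painful. With few keloids, a small gap or a large SD, R² can fall below 0.0143, and adjustment then costs slightly. This also stands. A reader might infer a large gain, such as power of 0.914 at R² = 0.3, but no share-and-gap combination in the table above gets beyond R² = 0.111.

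A reader might also infer that narrower intervals would let the trial support its Section 2 hypothesis that pain is unchanged without lidocaine. The documents do not support that. Section 10 sets no equivalence margin and powers a test to reject equality; a change of a few percent in width does not alter what that design can show.

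Finally, the choice of keloid alone can be questioned, since site, age and comorbidities are recorded too, and the lidocaine effect might differ by indication. Keloid is the recorded indication for which the Background itself makes a pain claim, and one binary term suits 73 patients. The model estimates an average effect and does not address interaction; that limit remains.

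**Conclusion.** The point holds as a cheap improvement of low severity. Section 10 plans a valid comparison and makes no use of a baseline factor that the protocol itself links to pain.

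A precision gain is expected from the Background's own statement but is not guaranteed. At an assumed R² of 0.05 to 0.10 the interval narrows by about 2% to 4%, with power of 0.814 to 0.835 if SD 0.3 and a difference of 0.2 hold. At R² = 0 the loss is about 0.6 power points and 0.7% of interval width. The relative widths rest only on the sample size and the assumed R²; the power figures also rest on the stated SD.

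The support is for pain at injection and up to several hours afterwards. The Background gives no basis for a keloid effect at 24 hours. Adjustment corrects no bias and would not rescue the sample size if the true SD were well above 0.3.

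**What to change.** Add to Section 10, in words such as:

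> Pain rated immediately after the injection will be compared between arms with a linear model containing treatment and indication (keloid vs other). The adjusted difference in means will be reported with its 95% CI, and the unadjusted difference with its 95% CI alongside. If no keloid patient is enrolled, the model reduces to the two-group comparison.

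The immediate rating fits the aim in Section 2: "The purpose of this study is to see if removing lidocaine from intralesional injections decreases pain of the injection". Which of the three ratings is the main result is a separate decision that this change does not settle. The same model can be applied to the 6-hour and 24-hour ratings, with no keloid effect presumed at 24 hours.

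The cost is wording and one degree of freedom. Indication is already collected, and neither enrolment nor procedures change.

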Day 1 (after clinic): Approximately 6 hours after the injection, a different study investigator will call the patient by phone to assess their current pain level with the visual analog scale. Using a different investigator who is unaware of the treatment arm for follow-up will further ensure blinding. Specifically, the investigator will say "Rate your

current pain level from the injection on a scale of 0 to 10, 0 being no pain and 10 being the worst pain of your life". Patients will be called up to three times before being considered lost to follow-up.

Day 2: Approximately 24 hours after the injection, the study investigator will again call the patient by phone to assess their current pain level with the visual analog scale. Specifically, the investigator will say "Rate your current pain level from the injection on a scale of 0 to 10, 0 being no pain and 10 being the worst pain of your life". Patients will then be thanked for their involvement in the study and encouraged to reach out to the principle investigator or clinic should any problems arise. Patients will be called up to three times before being considered lost to follow-up.

7. Risks

This study is categorized as less than minimal risk. We are comparing two treatment methods that are accepted as standard of care, and are already used on the clinic population being studied on a daily basis. There is no new experimental intervention that would put patients at greater than minimal risk. Although rare, the risks of a corticosteroid injection include hypopigmentation, skin atrophy, and hyperglycemia in patients with diabetes. There is also a small risk of an allergic reaction to the lidocaine component. There may be unknown or unanticipated adverse effects.

8. Reporting of Adverse Events or Unanticipated Problems Involving Risk to Participants or Others

Adverse events will be reported to the IRB immediately through standard reporting mechanisms.

9. Study Withdrawal/Discontinuation

There are no anticipated circumstances under which subjects would be withdrawn from research without their consent. If subjects withdraw, there will be no penalty or consequences.

10. Statistical Plan

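### Section 10 sizes the trial for 1.1538 controls per experimental subject while Section 5 allocates 50:50 by coin flip: an unexplained mismatch with almost no effect on power

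*Combined protocol and SAP*

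**What the plan says.** Section 5 (Enrollment/Randomization) sets the allocation rule: "Using a coin flip, patients will have a 50% chance of receiving one of the following treatments". The two treatments are corticosteroid with lidocaine and corticosteroid with normal saline.

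Section 10 (Statistical Plan) assumes "1.1538 control(s) per experimental subject", a standard deviation of 0.3, a true difference of 0.2, a Type I error of 0.05 and power of 0.8. It concludes that "we will need to study 34 experimental subjects and 39 control subjects". It states neither the sidedness of the test nor which treatment is the control. Section 2 gives an indication: "The purpose of this study is to see if removing lidocaine from intralesional injections decreases pain of the injection". That points to the lidocaine arm as control, but it is an inference.

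Section 12 sets the end of enrolment: "The study will last for approximately 1 year after initiation or until the enrollment goal is met". It does not say whether the goal is a total or a number per arm.

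On blinding, Section 6 says of the clinic visit: "A co-investigator will prepare the syringe to ensure blinding". For the rating taken straight after the injection it says: "Specifically, the co-investigator will say", followed by the 0 to 10 pain question. For the telephone calls it adds: "Using a different investigator who is unaware of the treatment arm for follow-up will further ensure blinding".

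**The concern.** A sample size should be worked out for the allocation that the trial will use. Here the ratio in Section 10 is not the ratio in Section 5, and no section describes or justifies unequal allocation. The ratio is also not a by-product of rounding the arm sizes: 39/34 = 1.1471, whereas 1.1538 = 15/13. It went into the calculation as an input.

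Two things could follow. The stated power might not apply to the trial as randomised. And the enrolment goal becomes ambiguous: staff could read it as 73 in total or as 34 and 39 in particular arms, and a later reader of unequal arms could not tell plan from chance.

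**Working it through.** **Inputs.** All from Section 10: SD s = 0.3, difference d = 0.2, alpha = 0.05, ratio 1.1538, arms 34 and 39. From Section 5: probability 0.5 for each arm.

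**Formula.** Power of the two-sample t-test from the noncentral t distribution with df = n1 + n2 − 2 and noncentrality d / (s × √(1/n1 + 1/n2)), two-sided.

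**Step 1: the plan's own figure.** For 34/39 the noncentrality is 0.2 / (0.3 × √(1/34 + 1/39)) = 2.841, df = 71 and the critical value is 1.994. Power is 80.03%. A one-sided test would give 87.9%, so the stated 0.8 is two-sided. At a ratio of 1.1538, the unrounded solution for 80% is 33.88 and 39.09, a total of 72.97. The plan's numbers reproduce.

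**Step 2: the same calculation at 1:1.** The unrounded solution is 36.31 per arm, a total of 72.61. The totals differ by 72.97 − 72.61 = 0.36 of a patient.

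| Split | Total | Power |
|---|---|---|
| 34/39 (plan) | 73 | 80.0% |
| 36/37 | 73 | 80.2% |
| 36/38 | 74 | 80.7% |
| 37/37 | 74 | 80.8% |

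**Step 3: the coin flip itself.** Simple randomisation does not fix the split. Assume that enrolment stops at a fixed total N, so that one arm's size is Binomial(N, 0.5), and average the power over the splits:

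- N = 73: 79.66%, which is 80 − 79.66 = 0.34 points short.
- N = 74: 80.22%.
- Ends of the central 95% of splits: 28/45 at N = 73 gives 78.0%; 29/45 at N = 74 gives 78.9%.
- A split at least as uneven as 34/39, in either direction, has probability 0.64 at N = 73.

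The small shortfall at 73 comes from chance imbalance, not from the ratio of 1.1538: an even split of the same total exceeds 80%.

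**Step 4: who takes the immediate rating.** Section 6 introduces a co-investigator who prepares the syringe, and a few lines later has the co-investigator, with the definite article, ask for the rating. The natural reading is that they are one person, who would know the arm. An arm-unaware assessor is promised only for the calls at about 6 and 24 hours.

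**The case against.** The strongest reply is that nothing depends on the ratio. It was used only for sizing, so it alters neither the allocation nor the comparison. The arm sizes are right for their stated inputs, the total is right for 1:1 to within one patient, and a split as uneven as 34/39 is an ordinary result of 73 coin flips. Moving from 73 to 74 also relies on an SD and a difference that Section 10 does not tie to the 0 to 10 rating, with no allowance for loss. All of this stands, and it is why the ratio is graded minor.

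A reader might infer more than the documents support:

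- **That the trial is underpowered.** The average of 79.7% requires a fixed total of 73, which Section 12 does not state. If enrolment continued until both arms reached their stated numbers, there would be no shortfall. It is true that 48% of 73-patient coin-flip trials have a split giving under 80%, but this reflects where the threshold falls: 33/40 gives 79.85% and counts as a miss, while 34/39 gives 80.03% and counts as a pass.
- **That Section 10 is miscalculated or the comparison biased.** Step 1 reproduces the figures, and a 50:50 coin flip is unaffected by a planning ratio.
- **That the immediate rating is certainly unblinded.** Section 6 reads that way but does not say outright that the two mentions are the same person.

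It is also fair to object that the rater and the coin flip are separate matters. They are, and they are offered below as separate improvements, not as consequences of the ratio.

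**Conclusion.** The inconsistency between Sections 5 and 10 is real, unexplained and minor. On the plan's own inputs, power is 80.0% at 34/39 and 80.2% at 36/37. The only shortfall is 0.3 points on average, under simple randomisation stopped at an assumed fixed total of 73. These figures take the SD of 0.3 and the difference of 0.2 as given, assume a two-sided t-test, and count patients with a rating; the documents give no loss rate, so none is added.

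Correcting the ratio is a matter of consistency and of a clear enrolment goal. More is to be gained from the two neighbouring points: the immediate rating is not protected by an arm-unaware assessor, and the coin flip as described provides neither concealment nor a record that can be checked.

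**What to change.** **Correction.** Restate Section 10 as 1:1 allocation with a two-sided test, and either

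- 73 patients with balanced allocation (36/37, 80.2%), or
- 74 patients (37 per arm, 80.8%; 80.2% on average if the coin flip stays).

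Give that total in Section 12 as the enrolment goal, alongside the existing limit of about one year. Name the control arm in the same edit. Cost: one or two sentences and at most one more patient.

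**Separate improvements, which carry most of the value.**

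1. Have someone already present and unaware of the arm ask for the immediate pain rating, and say so in Section 6. Cost: a small change of clinic roles, since that person must be there at the time of injection. No new staff are needed.
2. Replace the coin flip with a pre-generated 1:1 list in randomly varying blocks of 4 and 6, held in sequentially numbered opaque envelopes opened after consent. Allocation is then concealed, checkable and nearly balanced. At 74 patients the arms differ by at most 2 (36/38, 80.7%). At 73 they differ by at most 3 (35/38), which lies between the 34/39 and 36/37 splits and so keeps power between 80.0% and 80.2%. Cost: preparing the list and envelopes.

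### Section 10's difference of 0.2 and SD of 0.3 have no unit, time point or identified source, so the claimed 80% power cannot be tied to the 0–10 pain rating

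*Combined protocol and SAP*

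**What the plan says.** Section 10 is the whole statistical plan. It describes an unnamed continuous response compared between two independent groups, with 1.1538 controls per experimental subject, type I error 0.05 and power 0.8. The two inputs that set the sample size are the SD ("In a previous study the response within each subject group was normally distributed with standard deviation 0.3") and the target ("If the true difference in the experimental and control means is 0.2"). The result is 34 experimental and 39 control patients.

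Section 6 defines the measurements. At the visit, "Immediately following the injection, the patient will be asked to rate the pain of the injection", and the spoken question asks for a rating "on a scale of 0 to 10, 0 being no pain and 10 being the worst pain of your life". The same range is used in two telephone calls. The first is described as "Approximately 6 hours after the injection, a different study investigator will call the patient by phone to assess their current pain level"; the second comes at about 24 hours. Section 10 does not say which of the three ratings it powers.

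Section 1 sets the population: "This study will examine intralesional corticosteroid injections for keloids, alopecia areata, and other indications while including a wider variety of injection sites". The same section says that "Keloid injections are often more painful than other injections". Section 2 states the expectation: "We hypothesize there will be no difference in pain outcomes if lidocaine is removed from intralesional corticosteroid injections".

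**The concern.** A power statement has meaning only on the scale of the outcome. Here a reader cannot tell whether 0.2 and 0.3 are points on the 0–10 rating or something else, which rating they describe, or where they come from. Sections 1 and 3 describe a keloid trial and a trigger-finger study, but give no SD or mean difference for either, and Section 10 names neither as its source.

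Read as points, the figures are hard to accept. A normal distribution with SD 0.3 puts about 95% of an arm within 0.6 point of its mean on an 11-point range. The trial deliberately mixes indications and sites, and the protocol itself expects them to differ in pain.

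This matters most for the result the investigators expect. Section 2 hypothesizes no difference, while Section 10 plans only a test that can reject equality. A non-significant result is informative only to the extent that the reader knows, in rating points, which differences it leaves open.

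**Working it through.** **Inputs from Section 10:** difference 0.2, SD 0.3, alpha 0.05, power 0.80, 34 experimental and 39 control patients. Sidedness is not stated. Two-sided is inferred because it reproduces the sample size; a one-sided calculation by the normal approximation gives 26 + 30.

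**1. The plan's own figure.** Standardised difference = 0.2/0.3 = 0.667. Standard error = SD × √(1/34 + 1/39) = 0.3 × 0.2346 = 0.0704. Non-centrality = 0.2/0.0704 = 2.84 on 34 + 39 − 2 = 71 degrees of freedom. Two-sample t power is 80.0%. With 33 experimental patients and controls in the stated ratio it is 78.9%, so 34 is the smallest number that reaches 80%. The calculation is correct. A near-equal split such as 36/37, which the coin flip in Section 5 could produce, gives 80.2%, so the unequal ratio does not affect this point.

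**2. What 34 + 39 deliver if 0.2 means points.** The documents give no SD for the 0–10 rating, so every SD below except 0.3 is an assumption.

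- Non-centrality = 0.2/(SD × 0.2346)
- Detectable difference at 80% power = 0.666 × SD
- 95% CI half-width = t(0.975, 71) × SD × 0.2346 = 1.994 × 0.2346 × SD = 0.468 × SD

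| SD (points) | Non-centrality | Power for 0.2 | Detectable at 80% | 95% CI half-width |
|---|---|---|---|---|
| 0.3 | 2.84 | 80% | 0.20 | 0.14 |
| 0.35 | 2.44 | 67% | 0.23 | 0.16 |
| 0.5 | 1.70 | 39% | 0.33 | 0.23 |
| 1 | 0.85 | 13% | 0.67 | 0.47 |
| 2 | 0.43 | 7% | 1.33 | 0.94 |
| 3 | 0.28 | 6% | 2.00 | 1.40 |

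**3. Whether an SD of 0.3 point is credible.** Suppose patients answer in whole numbers, which is an assumption. If an arm's mean lies a fraction f above a whole number, its SD is at least √(f(1 − f)). An SD of 0.3 requires f(1 − f) ≤ 0.09, so the mean must lie within 0.1 of a whole number. Two such arms with means 0.2 apart must then sit exactly 0.1 either side of the same score. In each arm 90% give that score; the other 10% give the score just below in one arm and just above in the other. That is not the normal distribution Section 10 assumes. Scores bunched near zero at 24 hours could have a small SD, but they would not be normal either.

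**4. If the inputs are on another scale.** Power depends only on the ratio 0.2/0.3, so rescaling both leaves 80.0%. As one example, not found in the documents, fractions of the full scale would mean a difference of 2 points with SD 3, again 80.0%. The detectable difference would then be ten times the one the text appears to state.

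**The case against.** The strongest reply is that Section 10 is internally correct and that nothing in the documents contradicts an SD of 0.3. That stands. A reader might infer that the trial is shown to be underpowered, or that the sample size is wrong. The documents support neither, because every SD that produces a shortfall is an assumption.

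A reader might also try to quantify the loss by adding a keloid-versus-other gap to a within-indication SD of 0.3. Section 10 gives 0.3 as the SD of each whole group, and the protocol states neither the size of the gap nor the share of keloids. The mixture is therefore a reason to doubt 0.3 point, not a basis for a number.

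Nor do the documents say that the inputs are fractions of the scale. Every rating instruction says 0 to 10, and a transformed response is equally unstated. The tenfold contrast illustrates the ambiguity; it is not a contradiction within the plan. The scale in Appendix A cannot be seen, which limits what can be said about how ratings are recorded, although a drawing of the scale would hardly supply the source of the SD or the powered time point.

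Finally, the protocol does not say that a non-significant result will be read as no difference. The concern is that nothing in the plan guards against that reading, while Section 2 invites it.

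**Conclusion.** The point holds as a conditional one. It is certain that 0.2 and 0.3 carry no unit, time point or identified source, and that the powered rating is not named. High confidence applies to that part only.

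The consequence for power depends on the scale. If the inputs are 0–10 points, 80% power for 0.2 requires an SD of about 0.3 point. That is implausible for this mix of patients, though not disproved, and power is already down to 67% at an assumed SD of 0.35 and 39% at 0.5. If the inputs are on another scale, 80% may be correct, but for a difference the reader is not told.

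What can be relied on at any SD, with all 73 ratings available, is 80% power for about 0.67 SD and a 95% CI half-width of about 0.47 SD. At an assumed SD of 2 points the interval is about ±0.94 point, so a non-significant result could not exclude a difference of 0.2 point.

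**What to change.** Rewrite the paragraph in Section 10:

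1. Name the rating that is powered, for example the one immediately after injection.
2. Identify the previous study, and give the unit and time point of 0.3 and 0.2. If they come from another scale, convert them to 0–10 and say so.
3. At the planned 34 + 39, restate the detectable difference as about 0.67 SD with 80% power. Express it in 0–10 points using an SD from an identified study on that scale and at that time point (0.67, 1.33 or 2.0 points at SD 1, 2 or 3). Say whether a difference of that size is meaningful, so that the target is justified and not merely derived from the existing N.
4. Report the mean difference in points with its 95% CI. State that a non-significant result will not be taken as support for the no-difference hypothesis in Section 2.

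**Cost:** one paragraph, a search for a usable SD, and no extra patients. The restated detectable difference will probably look less favourable than 0.2. If 0.2 point really is the target, N must be recomputed. By the same t calculation at 80% power and a 34:39 ratio, it would be about 200 patients at an assumed SD of 0.5 (93 + 107), 791 at SD 1 (368 + 423) and 3,157 at SD 2 (1,470 + 1,687).
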